9. STATISTICAL CONSIDERATIONS

C3FIT will compare the effectiveness of the JC-certified CSC/PSC care system with the ISPU care system in improving patient outcome and quality of life post-stroke. The primary outcome is the SIS-3.0 at 12 months, while assessment at 3 and 6 months are part of secondary outcomes. The primary analysis will focus on intervention differences in mean SIS score at 12 months. Mixed models will be used to assess the SIS outcome at 12 months, allowing the hierarchical nature of the data to be reflected (patients within Sites), and providing an accounting for data that are not missing completely at random. We anticipate (and trust) that randomization will balance potential confounding factors; however, secondary analysis will be performed with adjustment for baseline factors that could be imbalanced and potentially confound the estimated intervention differences, specifically adjusting for factors assessed at baseline that are known to be strongly associated with stroke outcomes (specifically age and stroke severity). Patients who die or cannot return due to morbid conditions will be assigned to “floor” score for poor outcome (and hence does not reduce the number of evaluable patients). With these patients not representing missing data, we anticipate there will be relatively little additional missing data and that these data will be generally missing at random (i.e., patients not returning because of other conditions, like moving); however, missing data that is present will be addressed by including baseline, 3, and 6 month data in the model and allowing the mixed model to adjust estimates for the missing data at 12 months by incorporating information available through the correlation between measurements.

A. Sample Size

The total sample size for the primary outcome for this study will be approximately 1,800 patients (each arm anticipated to have approximately 900 patients with approximately 100 patients at each clinical site, although some sites will enroll up to 140 consented participants due to limited enrollment by other sites due to institutional COVID PANDEMIC issues). We have intentionally restricted clinical site participation to those Sites certified as a TJC CSC/PSC (or acting as such). This restriction is important not only to provide CSC/PSC intervention “state of the art” comparator group, but also to increase the homogeneity of Sites and, thereby, reduce intraclass correlation coefficient in the hierarchical models. We do not have information on the intraclass correlation coefficient of the SIS, but given this restriction, we would suggest it is quite small (0.01); however, for power calculations, we have conservatively assumed it is of modest size (0.05) and also provide estimates should it be large (0.10). These larger intraclass

correlations would arise if there is larger than anticipated heterogeneity of intervention effect, and that there is adequate power for these larger intraclass correlation coefficients shows that we are well-positioned to detect intervention even in the presence substantial heterogeneity of the effect. Under this assumption and with the standard deviation of the SIS being approximately 8⁴⁹, if the interclass correlation is 0.05 then mean intervention differences of 2.7 and 3.2 can be detected with 80% and 90% power respectively (power calculations by PASS, NCSS, Kayville, UT); 2.7 was chosen based on evidence from Lin et al³⁰. Even if the intraclass correlation is 0.10, differences of 3.7 and 4.3 can be detected with 80% and 90% power. As such, we have quite good power to detect clinically significant differences generally smaller than half of a standard deviation of the outcome scale.

B. Analyses

Analysis of the primary analysis will focus on intervention differences in mean SIS and smRS scores at 12 months. In addition, the mixed models will be used to assess the SIS and smRS outcomes at 12 months, allowing the hierarchical nature of the data to be reflected (patients within Sites), and providing an accounting for data that are not missing completely at random. Analyses of the secondary outcomes of time either rehospitalization or subsequent stroke will be assessed using proportional hazards analysis. In order to incorporate the hierarchical nature of these data, this analysis will be implemented using packages such as the SURVIVAL procedure from the SUDAAN package (Research Triangle Institute, Research Triangle Park, NC).

Analysis of the QOL secondary outcome will follow the analysis approach as the primary analysis and will have similar power (i.e., ability to detect intervention differences of magnitude of a half-standard-deviation). The study will also focus on identifying specific subgroups who are particularly responsive or resilient to intervention differences.

10. HUMAN SUBJECTS PROTECTIONS

This protocol and the informed consent document (Appendix A) and any subsequent modifications will be reviewed and approved by the Steering Committee, IRB, and DSMB responsible for oversight of the study. A signed consent form will be obtained from the subjects.

The total sample size for the primary outcome for this study will be approximately 1800 patients (approximately 100 patients at each clinical site, although some sites will enroll up to 140 consented participants due to limited enrollment by other sites due to institutional COVID PANDEMIC issues) who have consented to participate.

- Participating patients at a clinical site randomized to ISPU arm will be followed by Stroke Central to collect the same acute in-hospital metrics to measure care quality, health status, and outcomes and will also be contacted via telephone by the blinded personnel at the UAB SDCC SRU to assess primary outcomes. However, ISPU patients will also be assessed monthly by Stroke Mobile for 1-year in their home to collect specific metrics that will evaluate the patient and caregiver/family for potential issues and provide follow-up care and targeted education and support.
- The patient and their caregiver (or their legally authorized representative, if patients are unable to provide consent) will be approached to participate in the study ideally during hospitalization or within 5 business days of hospital discharge ideally (to a

maximum of 14 total days) to allow for data collection of specific acute in-hospital metrics. Caregivers may be consented at any time during the C3FIT study, but no data will be collected until consent is obtained. At research visits, the following will be obtained: (1) demographic and other data collection; (2) follow-up data collection specific to the ISPU arm; and (3) contact via telephone survey to collect SIS and smRS outcome data.

- C3FIT's population will include patients with all stroke subtypes and levels of severity, regardless of gender, race, ethnicity, or socioeconomic status. Each Site will recruit from their geographically eligible patients (who have a discharge diagnosis of stroke according to their ICD-10 code) until approximately 100 patients are consented, although some sites will enroll up to 140 consented participants due to limited enrollment by other sites due to institutional COVID PANDEMIC issues.

A. Adequacy of Protection Against Risks

Recruitment and Informed Consent. The acute in-hospital study sample will include patients admitted to the hospital with suspected stroke symptoms. Potential participants (both patient and caregiver if available) will be approached for recruitment ideally within 5 business days post discharge ideally (to a maximum of 14 total days) for the participant. In the event that the patient is unable to provide consent, their surrogate can be consented. Patients will be identified by study personnel from ED and stroke service admission logs; pilot data suggests nearly complete case ascertainment. To assure that acute in-hospital recruitment and informed consent procedures are followed consistently across Sites, a guidance document will be prepared in consultation with Site PI's and other patient, caregiver and organizational stakeholders, and Site personnel will be trained consistently by CCC staff.

The post-hospital discharge study sample will include patients and caregivers who have a discharge diagnosis of stroke and who reside in each clinical site's defined geographic area. Potential participants will be approached prior to hospital discharge regarding their interest in participating in the study, and every effort will be made to consent both patient and caregiver at that time.

Patients and caregivers at an ISPU Site who participate in Stroke Mobile will receive 12 in-home visits from Stroke Mobile. At each visit, Stroke Mobile will conduct a physical assessment and administer specific clinical scales to determine functional status, medication adherence, fall risk, daily activity level, depression, and caregiver strain, among others. A phlebotomy (draw blood) will occur (cholesterol and HbA1c) according to the study time schedule.

The consent process will begin at hospital admission at a C3FIT clinical site. The PI at the site or his/her Co-I designee will provide information to the patient and/or caregiver about the nature of the trial, the two arm comparator groups and the randomization of the site. The fact that the C3FIT study does not involve an investigational drug or device will be discussed with the patient and caregiver. Potential participants will be made aware of the scientific basis for the comparison of methods of care delivery, and the clinical equipoise of the investigators. Information on the requirements of the participants will be discussed: (1) to allow appropriate outcome scales to be obtained, (2) the approximate time involved in obtaining these scales based on or pilot experience, (3) that some of the outcome scales will be obtained by phone by

blinded interviewers at the UAB SDCC SRU, (4) and that common laboratory tests will be obtained that would be appropriate for monitoring any person who suffered a stroke.

Potential and enrolled participants will: (1) be assured that they may withdraw consent at any time and do not have to provide a reason for their withdrawal; (2) have the right to speak with a member of our patient/stakeholder advisory group if they so choose to obtain additional information; and (3) be provided access to study personnel at their C3FIT clinical site (including the PI) to answer any questions or address concerns. In addition, the C3FIT personnel at the CCC are available for any questions or issues they identify. Potential participants will be assured that study personnel will be well trained, are familiar with guidelines for human subject's protection, and will have completed appropriate human subject's protection training as required by their site and the C3FIT Central IRB. A member of the Stakeholder Committee for C3FIT is a medical ethicist who has assisted in the design of the pilot study and, as such, will be available as a resource to C3FIT study personnel if specific ethical issues arise.

B. Potential Risks to Subjects and Protections

Potential risks for C3FIT participants and proposed methods to reduce these risks are described below. A member of the Stakeholder Committee for C3FIT is a medical ethicist who has assisted in the design of the pilot study and, as such, will be available as a resource to C3FIT study personnel if specific ethical issues arise.

- 1) *Breach of confidentiality of medical information in the acute in-hospital or outpatient setting – minimal risk.* All data will be stored in encrypted, password-protected databases that meet mandated IT security standards and will include subject identifiers (name, address, date of birth, and medical record numbers) necessary to maintain contact during the study.
- 2) *Anxiety/discomfort – minimal risk.* Participants will be assured that all study-related data and information (including both outcome assessment and monitoring data) will be kept confidential by the PI and study personnel, any questions and concerns can be addressed at any time, and participants can refuse to answer any question or not participate at any time during the study.
- 3) *Harm from physical and clinical assessments or measurements conducted as part of the outpatient ISPU program – minimal risk.* Physical assessments like the National Institutes of Health Stroke Scale and smRS are standard clinical assessment scales utilized in clinical practice. C3FIT study personnel will undergo training and certification in these scales, which have no recognized physical harm. Other scales used, including the primary outcome scale (SIS), have been used in many clinical situations/studies with no recognized harm.
- 4) *Discomfort and/or harm from blood draws to assess cholesterol level and HbgA1c – minimal risk.* Standard phlebotomy techniques will be used as in typical care. The minimal pain and risk of fainting will be acknowledged to potential participants, and participants may decline some or all of the blood draws.

Since no investigational device is involved in the C3FIT study, we anticipate few adverse events. However, our conservative approach is to provide several layers of protection for our study participants: (1) the informed consent process itself; (2) access to the C3FIT personnel, including the C3FIT nurses and physician Site PI; (3) access to the CCC staff, including the C3FIT

PI; (4) a Central IRB at Vanderbilt to provide consistency across 18 C3FIT Sites; and (5) a Data and Safety Monitoring Board (DSMB) that will review patient outcome data; and (6) human subjects research protections using the CITI certification as required by the Central IRB.

Adverse events (physical, behavioral, or psychological) will be reported to the Clinical Site PI or the SDCC; they will report these adverse events per guidelines in a timely fashion to the CCC, where they will be reviewed by the PI, Project Manager and forwarded to the DSMB.

C. Potential Benefits of the Proposed Research

Benefits for Patients. The major benefit to patients will accrue to future patients who benefit from the information gained from this study to design a patient-centered stroke healthcare delivery system that is comprehensive, integrated, and caregiver/family-focused. Many of the current issues faced by stroke patients involve lack of defect free stroke care in the in-hospital phase of care, leading to longer lengths of stay and in-hospital complications. These complications can lead to loss of QOL over many years. Lack of defect free care also plagues the post-hospital phase of care where stroke recurrence leads to readmissions and less Time at Home. Patients can also benefit by access to results of C3FIT to inform their choices in health care based on data that identifies the most effective and efficient care.

Based on positive results of C3FIT, patients could also benefit by having the potential for home care management, avoiding time and travel costs for outpatient clinic visits. Patients will have screening for HbA1C and cholesterol to measure risk factor control at-target which may help identify targets of therapy. Patients could also benefit by having their caregivers supported by study personnel reducing caregiver strain. Because patients are involved in the design, implementation and dissemination of C3FIT outcomes that matter to them will be foremost in the study design.

Benefits for Caregivers. The major benefit to caregivers will accrue to future caregivers where the information gained from this study can be used to design a patient-centered stroke healthcare delivery system that is comprehensive, integrated, and caregiver/family-focused. Such a system may encourage recovery in their associated patient and limit stroke recurrences and readmissions.

If results from C3FIT are positive, caregivers could have the potential advantage of home visits, avoiding the stress, time commitment, and travel costs of clinic visits. Caregivers could potentially benefit by having a team that monitors their stress level and offers support.

Benefits for Organizational Stakeholders and Society. Organizational stakeholders will benefit by having access to high quality data to inform decisions regarding design and implementation of the most efficient and effective stroke delivery system.

D. Risk-to-Benefit Ratio

C3FIT risks to participants are reasonable. C3FIT does not involve any investigational drug or device, so the risks of unknown or unrecognized side effects of investigational drugs and devices are not an issue. C3FIT involves several blood specimen collections (HBA1C and cholesterol) with associated pain from the needle stick. This discomfort is transient and considered minimal. These tests would be considered standard of care in a stroke patient. The collections themselves are to obtain lab values that will be used to document control at target of risk factors and inform decisions about best medication or other therapy based on nationally

accepted guidelines. Testing procedures involve only grading scales often used in practice (i.e., NIH Stroke Scale, Simplified Modified Rankin Scale (smRS), or scales that are commonly used in stroke clinical trials for outcome). The information requested will include some information about sexual, urinary, and bowel function but will be obtained by trained medical personnel with a minimum of patient distress. The time involved in obtaining information from patients and caregivers is carefully considered. Only those scales determined critical to patient management and documentation of key functional and QOL outcomes are utilized. The timing of administration of these scales is also carefully chosen to not provide undue time commitment or stress at any visit. Given the minimal risks and significant potential benefits the risk benefit ratio seems reasonable and quite acceptable.

Importance of the Knowledge to be Gained. We have discussed the opportunity to improve stroke care delivery given the lack of defect free care, complications, recurrences, and lack of risk factor control documented for stroke patients. In addition, the opportunity to focus on stroke outcomes that are patient-centered will significantly improve patient and caregiver engagement in their intervention and recovery journey resulting from stroke. Organizational stakeholders such as the JC and the ASA, who are tasked with offering improvement programs that are informed by high quality scientific evidence, will find data from C3FIT invaluable, as Level 1 evidence to assist in identifying the appropriate focus for resources and effort does not currently exist. Vascular neurologists (VNs) and rehabilitation and internal medicine physicians will find that the results of this trial will help design care delivery approaches that provide the most appropriate patient centered functional and QOL outcomes rather than depending on compliance with process measures that may not contribute to these more important outcomes.

As in any research effort, much of the time, stress, and risk of the project is born by participants. It is hoped that including them as Research Partners may help to ally some of this burden. In any event, they are to be honored for their involvement.

Data and Safety Monitoring Plan. A formal Data and Safety Monitoring Board (DSMB) will be convened at regular intervals (for example, twice a year) to review and monitor recruitment, data security, and patient safety. The DSMB and development of the formal DSMB Plan is described in Section 8.

ClinicalTrials.gov. This randomized trial will be registered, and results will be reported in ClinicalTrials.gov as encouraged by NIH and required by Public Law 110-85.

E. Inclusion of Women and Minorities

This study has no exclusion criteria based on gender, race, or ethnicity. We anticipate that patients recruited to our study will reflect the demographic profile of the general stroke population, which proportionally includes more older adults than younger and good representation of minorities. While the age-adjusted incidence of stroke (primarily ischemic stroke) in men is approximately 30% higher than in women, because women live longer than men, more women have stroke than men. However, because they are older at time of stroke, women have more co-morbidities so they may be less likely to meet some of inclusion/criteria.

F. Subject Confidentiality

All laboratory specimens, evaluation forms, reports, video recordings, and other records that leave the site will be identified only by the Study Identification Number (SID) to maintain

subject confidentiality. All records will be kept in a locked file cabinet. All computer entry and networking programs will be done using SIDs only. Clinical information will not be released without written permission of the subject, except as necessary for monitoring by IRB, PCORI, or the DSMB.

G. Study Modification/Discontinuation

The study may be modified or discontinued at any time by the IRB, PCORI, or the DSMB as part of their duties to ensure that research subjects are protected.

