(7) Exercise	Question(s) to assess patient adherence to recommendations of the AHA.	X	X ⁺	X ⁺	X ⁺
Mortality*	Will be assessed at visits. If needed, medical records will be collected from site, and the Adjudication Committee will review.		X	X	X
Recurrent Stroke*			X	X	X
Rehospitalization*			X	X	X
Time at Home	Assesses Time at Home (patient or caregiver home) versus at institution (for hospitalization, IPR, and/or SNF).		X ⁺	X ⁺	X ⁺
Depression (Patient)	Patient Health Questionnaire (PHQ-9)		X	X	X
Caregiver Strain	Caregiver Strain Index		X	X	X
*Results of these measures will be reported back to patient's treatment team for information/action. *SRU only. H: Collected at the Hospital prior to discharge by site personnel IPR: In-patient rehabilitation facility SNF: Skilled Nursing Facility					

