6. BASELINE AND FOLLOW-UP ASSESSMENTS AND LABORATORY EVALUATIONS

The following outlines the Data Paradigms for Stroke Mobile based on obtained values for various scales and data points utilized. The guidelines establishing blood pressure and cholesterol goals are from the American Heart and Stroke Association.⁸

A. On-Study/On-Intervention Evaluations

The schedule of evaluations occurring after randomization while the subject is on-study and on (or about to start) intervention along with allowable time window in which evaluations may take place (± 30 days with a target of ± 14 days) is shown in Tables 7 and 8. Primary and secondary outcomes are considered a mandatory part of the protocol; remaining measures will be collected if patient/caregiver are able and/or available.

Table 7. Data Collection Paradigm: ISPU Arm, Stroke Central and Stroke Mobile

Item/Metric	In Hospital Prior to Discharge	Post Discharge Visit											
		Day 0-14	Month of Visit to Home/Facility										
		1	2	3	4	5	6	7	8	9	10	11	12
Informed Consent Confirmed	X	X	X	X	X	X	X	X	X	X	X	X	X
Demographics (Age, Gender, Race/Ethnicity, Marital Status, Zip Code of Residence, Income, and Education)*	X			X			X						X
Caregiver/Family identified*	X			X			X						X
Medical Record Number (MR #)*	X												
Get-With-The-Guidelines (GWTG) in-hospital data*	X												
Patient Medical History	X			X			X						X
Complications* ¹	X			X			X						X
National Institutes of Health Stroke Scale (NIHSS)*	X	X	X	X	X	X	X	X	X	X	X	X	X
Stroke Subtype*	X												
Prior stroke/Transient Ischemic Attack (TIA)*	X												
Risk factor profile* ²	X												X
Cholesterol panel or LDL*	X			X			X						X
Hemoglobin A1C (HBA1C)*	X			X			X						X
Perceived Support				SRU			SRU						SRU
Stroke Impact Scale (SIS)				SRU			SRU						SRU
Simplified Modified Rankin Scale (smRS)	X			SRU			SRU						SRU
Blood Pressure (BP) Control: at target	X	X	X	X	X	X	X	X	X	X	X	X	X
Lipid Control: LDL, at target	X			X			X						X
Diabetes Control: HBA1C, at target	X			X			X						X
Smoking Status	X	X	X	X	X	X	X	X	X	X	X	X	X
Body Mass Index (BMI)	X	X	X	X	X	X	X	X	X	X	X	X	X
Diet Assessment	X	X	X	X	X	X	X	X	X	X	X	X	X
Exercise Assessment	X	X	X	X	X	X	X	X	X	X	X	X	X
Mortality surveillance		X	X	X	X	X	X	X	X	X	X	X	X
Recurrence surveillance		X	X	X	X	X	X	X	X	X	X	X	X
Readmission surveillance		X	X	X	X	X	X	X	X	X	X	X	X
Time at Home		X		SRU			SRU						SRU
Depression History	X												
Depression: Patient Health Questionnaire (PHQ-9)		X	X	X	X	X	X	X	X	X	X	X	X

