5. MODEL OF CARE – THE CSC/PSC ARM

Post-discharge, management and treatment of patients in the CSC/PSC arm will follow general clinical practice guidelines as is usually provided by the site in the management of all patients following a stroke, e.g. one-month clinic follow-up by a vascular neurologist. Patients will return to the CSC/PSC site per protocol for data collection research visits at 3, 6, and 12 months, and the University of Alabama Birmingham (UAB) SDCC Survey Research Unit (SRU) will contact them by phone at these times (see Figure 4). No C3FIT intervention management will be provided at these visits, however, usual standard of stroke care will occur. If there are emergent needs, the patient will be referred to that site's emergency department, patient's family physician, or the physician PI at the site.

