6. BASELINE AND FOLLOW-UP ASSESSMENTS AND LABORATORY EVALUATIONS

The following outlines the Data Paradigms for the CSC/PSC arm based on obtained values for various scales and data points utilized. The guidelines establishing blood pressure and cholesterol goals are from the American Heart and Stroke Association.⁸

A. On-Study/On-Intervention Evaluations

The schedule of evaluations occurring after randomization while the subject is on-study and on (or about to start) intervention along with allowable time window in which evaluations may take place (± 30 days with a target of ± 14 days) is shown in Table 7. Primary and secondary outcomes are considered a mandatory part of the protocol; remaining measures will be collected if patient/caregiver are able and/or available.

Table 7. Data Collection Paradigm: CSC/PSC Arm

Item/Metric	In Hospital Prior to Discharge	Post Discharge Visit												
		Day 0-14	Month of Visit to Home/Facility											
			1	2	3	4	5	6	7	8	9	10	11	12
Informed Consent Confirmed	X			X			X						X	
Demographics (Age, Gender, Race/Ethnicity, Marital Status, Zip Code of Residence, Income, and Education)*	X			X			X						X	
Caregiver/Family identified*	X			X			X						X	
Medical Record Number (MR #)*	X													
Get-With-The-Guidelines (GWTG) in-hospital data*	X													
Complications* ¹	X			X			X						X	
Patient Medical History	X			X			X						X	
National Institutes of Health Stroke Scale (NIHSS)*	X												X	
Stroke Subtype*	X													
Prior stroke/Transient Ischemic Attack (TIA)*	X													
Risk factor profile* ²	X												X	
Cholesterol panel or LDL*	X			X			X						X	
Hemoglobin A1C (HBA1C)*	X			X			X						X	
Perceived Support				SRU			SRU						SRU	

Stroke Impact Scale (SIS)				SRU			SRU						SRU
Simplified Modified Rankin Scale (smRS)	X			SRU			SRU						SRU
Blood Pressure (BP) Control: at target	X			X			X						X
Lipid Control: LDL, at target	X			X			X						X
Diabetes Control: HBA1C, at target	X			X			X						X
Smoking Status	X			X			X						X
Body Mass Index (BMI)	X			X			X						X
Diet Assessment	X			SRU			SRU						SRU
Exercise Assessment	X			SRU			SRU						SRU
Mortality surveillance				X			X						X
Recurrence surveillance				X			X						X
Readmission surveillance				X			X						X
Time at Home				X			X						X
Depression: Patient Health Questionnaire (PHQ-9)				X			X						X
Caregiver Strain Index (CSI)				X			X						X

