## **4. Secondary Outcomes**

### **4.1. Time-to-event secondary outcomes (mortality, recurrent stroke, and rehospitalization)**

The number of days between discharge and death, recurrent stroke or rehospitalization will be calculated, and treatment differences in the times will be assessed using hierarchical proportional hazards models (i.e., using a RANDOM statement for site if conversion, or fixed effect with no conversion). The same incremental modeling approach (crude, adjusted for stroke severity, further adjusted for demographics, and finally adjusted for risk factors) will be employed. It is possible that the number of events may be relatively small (particularly for death and recurrent

stroke), introducing concerns for the use of too many covariates relative to the number of predictors. Should this be the case, a “restricted” number of covariates will be considered, specifically using NIHSS as the single index of severity, using age and race/ethnicity as the indexes of demographics, and hypertension as the single index of risk factors. These will be added in this order up to the point where there are at least 10 events for each factor introduced (i.e., perhaps, not even all these predictors can be considered).

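### Diet, exercise, time at home, recurrent stroke and readmission are scheduled to be collected differently in the two arms, which risks differential measurement bias that the SAP does not address

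*Protocol*

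**What the plan says.** **Contacts.** Protocol section 10 (ISPU version) says that "ISPU patients will also be assessed monthly by Stroke Mobile for 1-year in their home to collect specific metrics"; the same sentence gives these visits a care and education role. Section 10.A says that ISPU patients "will receive 12 in-home visits from Stroke Mobile". In the CSC/PSC version, section 5 says: "Patients will return to the CSC/PSC site per protocol for data collection research visits at 3, 6, and 12 months".

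**Diet and exercise.** In Table 7 for ISPU the diet row reads "Diet Assessment X X X X X X X X X X X X X": one in-hospital mark and 12 after discharge, none of them SRU. The key names Stroke Mobile for additional assessments. In Table 7 for CSC/PSC the row reads "Diet Assessment X SRU SRU SRU", with the SRU entries at 3, 6 and 12 months. The exercise rows match the diet rows. Table 8 (ISPU) also has Stroke Mobile discuss diet and exercise at each visit.

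**Table 1** (section 1.B, both versions) puts a plus sign on diet, exercise and time at home at 3, 6 and 12 months. The matching footnote appears to be the one that reads "SRU only. H: Collected at the Hospital prior to discharge by site personnel".

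**SAP.** Section 1 makes six intermediate factors, diet and exercise among them, integral to the primary assessment. Section 3.1 models them at 3, 6 and 12 months. Section 4.1 says: "The number of days between discharge and death, recurrent stroke or rehospitalization will be calculated". Section 4.2 analyses time at home. None of these sections says whether the SRU or the site supplies the data.

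**The concern.** If both Table 7s are followed as written, the diet and exercise comparisons set answers given to the team that counsels the patient against answers given to a telephone interviewer. Patients tend to report better adherence to their own coach, which would favour ISPU. The SAP's main analysis of these factors is restricted to patients not adherent at baseline, the group in which over-reporting can look like success.

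For recurrent stroke and readmission the difference lies in how often patients are asked. Monthly contact can pick up events that are forgotten over a three- or six-month interval, and this would count against ISPU.

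Time at home differs in assessor. The direction there is uncertain.

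Once the data are in, none of these effects can be separated from a treatment effect, and an unnamed source leaves a choice open until after the results are seen.

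**Working it through.** There is no stated figure to reproduce. The check is a row-by-row comparison of the tables, followed by illustrations on assumed values.

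**Step 1. Schedules side by side (post-discharge entries)**

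| Outcome | Table 1 | Table 7, ISPU | Table 7, CSC/PSC | What differs |
|---|---|---|---|---|
| Diet, exercise | apparently SRU at 3, 6, 12 | site mark at 12 visits | SRU at 3, 6, 12 | assessor |
| Time at home | apparently SRU at 3, 6, 12 | one site mark, then SRU at 3, 6, 12 | site mark at 3, 6, 12 | assessor (4 contacts against 3) |
| Recurrent stroke, readmission | 3, 6, 12 | 12 visits | 3, 6, 12 | frequency, 12 / 3 = 4 to 1 |
| Smoking, PHQ-9 | 3, 6, 12 | site mark at 12 visits | site mark at 3, 6, 12 | Stroke Mobile against coordinator |
| SIS, smRS | apparently SRU at 3, 6, 12 | SRU at 3, 6, 12 | SRU at 3, 6, 12 | nothing |

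Table 1 therefore contradicts the ISPU Table 7 on diet and exercise, and the CSC/PSC Table 7 on time at home. SIS and smRS carry the same plus sign in Table 1 and are marked SRU in both Table 7s, which supports reading that sign as SRU only.

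**Step 2. Does frequency matter for each outcome?** For diet and exercise the SAP uses months 3, 6 and 12 only, so the extra monthly visits add no data points; the issue is who asks. For events any contact can reveal one, so frequency matters directly.

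**Step 3. Illustration for diet or exercise (assumed rates).** Let p be the true follow-up adherence, equal in both arms, and f the share of non-adherent ISPU patients who report adherence. The spurious difference is (1 − p) × f.
- p = 0.20, f = 0.10: 0.80 × 0.10 = 8 points.
- p = 0.30, f = 0.10: 0.70 × 0.10 = 7 points.
- p = 0.40, f = 0.10: 0.60 × 0.10 = 6 points.
- With f from 0.05 to 0.20 over the same p, the range is 3 to 16 points.

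For scale, take all 1,262 patients at 21 sites: 631 per arm, 1262 / 21 = 60.1 per site, design effect 1 + 59.1 × ICC, which is 1.59 at ICC 0.01 and 3.95 at ICC 0.05. For f = 0.10, the chance of a false two-sided p < 0.05 is then 40% to 75% (ICC 0.01) or 19% to 39% (ICC 0.05). These chances are on the high side: the SAP's main analysis uses a smaller subset, and normal quantiles ignore the small number of sites.

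**Step 4. Illustration for events (assumed capture).** With a true ratio of 1, the apparent ratio is about capture in ISPU divided by capture in CSC/PSC.
- 0.95 / 0.90 = 1.06
- 0.95 / 0.85 = 1.12
- 0.95 / 0.75 = 1.27

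This treats missed events as unrelated to their timing, so it only approximates a hazard ratio.

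**Step 5. What in the plan could correct this?** Adjudication (section 8.B) covers stroke-related hospitalisations that were reported. Medical records are collected if needed. Inverse probability weighting (SAP 3.1) models whether the 12-month value is observed. None of these recovers an unreported event or corrects an answer shaped by who asked.

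**The case against.** The strongest reply is that Table 1 governs. If the SRU collected diet, exercise and time at home in both arms, that part is a table error and not a bias. The colour coding in Table 7 is also lost in the available text, so attributing the ISPU marks to Stroke Mobile is an inference, and section 6 says that ISPU final evaluations are shared between Stroke Mobile and the SRU. This stands in part. The same ISPU table labels SIS, smRS and time at home as SRU and leaves diet and exercise unlabelled, so the conflict is real and the SAP does not resolve it. The event schedules differ whichever table governs diet.

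On events, both arms are queried at 3, 6 and 12 months, with adjudication and records as support. That limits the problem but does not remove it.

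A reader might infer more than the documents support:
- That bias has been shown. No recall, capture or over-reporting rate is given anywhere.
- That 10% over-reporting means a 10-point difference. That holds only if nobody is truly adherent.
- That more frequent visits distort diet, exercise or time at home. The first two are analysed at three time points, and the third has 4 contacts against 3.
- That mortality is equally exposed. Its surveillance schedule also differs, but a death is unlikely to go unreported by the end of follow-up.

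**Conclusion.** The plan carries a risk of differential measurement bias, and the tables contradict each other. For diet and exercise the problem is the assessor; for recurrent stroke and readmission it is the frequency of contact; for time at home it is the assessor, with uncertain direction.

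The size cannot be derived from the documents. On the stated assumptions it is 6 to 8 points in favour of ISPU on diet or exercise (10% over-reporting, 20% to 40% truly adherent), and an apparent ratio of about 1.06 to 1.27 against ISPU on events (capture 95% against 90% to 75%). If Table 1 reflects practice, the diet, exercise and time-at-home part reduces to a documentation error and the event part remains.

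It would be wrong to infer that the SIS and smRS comparisons are compromised: their follow-up is scheduled through the SRU in both arms. This is an inexpensive improvement worth making, not a flaw in the trial's main result.

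**What to change.** 1. Reconcile Table 1 with both Table 7s, and state who collected each outcome in each arm.
2. In SAP 3.1 and 4.2, use SRU-collected 3-, 6- and 12-month data for diet, exercise and time at home in both arms. The SAP says that 21 sites have provided data, so correcting a table may not change what exists. Where SRU values are absent in one arm, report that outcome as unblinded and outside the primary assessment.
3. Flag the same assessor difference for smoking and PHQ-9, which are site-collected in both arms.
4. In SAP 4.1, analyse recurrent stroke and rehospitalisation with events ascertained the same way in both arms (the 3-, 6- and 12-month query plus records). Report the analysis with and without events known only from the extra monthly ISPU contacts.

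The cost is table corrections and SAP wording. No new patient contact is needed, because the SRU is already scheduled to call both arms. The downside is that events known only from monthly visits leave one of the two analyses; the documents do not show how many that would be.
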